# PHASE 3 RANDOMIZED CONTROLLED TRIAL

- 4.1.4 Phase III Randomized Controlled Trial. For the RCT, 300 participants meeting entry criteria will be enrolled over 13 months (approximately 23 per month). Participants will be randomized using a factorial design with the following factors:
- **4.1.4.1** Factor 1. Hub App with intelligent recommender system/Hub app without intelligent recommender system: This factor is consistent with Objective 2.1.3 on pg. 4
- **4.1.4.2** Factor 2. Coaching/No Coaching: This factor would allow us to examine and control for the effect of coaching.
- **4.1.5** *Phase III Enrollment.* Participants in the RCT will be enrolled remotely to avoid excluding individuals with access barriers who are among those who would be likely end users. Screening will be conducted in 3 stages.
- 4.1.5.1 Screening Stage 1 (pre-consent): Interested parties will complete a brief web screen to determine whether there is any reasonable expectation that they might be eligible (data from the brief screen will be included in the study dataset). If they are clearly not eligible they will be informed of this and thanked. If they appear to be eligible a research assistant will follow-up by phone to clarify responses from the web screen and ask additional phone screening questions. If the participant passes the stage 1 phone screen s/he will be invited to initiate the online consent process and proceed to screening stage 2 described below.
- 4.1.5.2 Online Consent/Screening Stage 2: The participant will be emailed a link to the detailed digital version of the consent form which will be deployed through REDcap or another secure online survey system. Subjects will read through the consent form, answer a series of questions to assess comprehension, and agree to participate by checking a box, typing in their name, and signing electronically. After the online consent form is submitted, participants will continue on to complete a set of baseline questionnaires which will further assess study eligibility. Once the questionnaires are submitted, study staff will review the participant's digital file to (1) ensure that the consent form was signed and the comprehension questions were answered correctly and (2) make an eligibility determination based on the questionnaire responses. If a participant answers any of the consent comprehension questions incorrectly, a research assistant will follow up to review that section of the consent form and explain the correct answer. Participants may contact study staff at any time for a copy of the consent form for their records. All participants who complete screening stage 2 will be notified regarding eligibility by phone or email. Ineligible participants will be thanked, sent a resource guide and compensated \$10 for completing the online questionnaire. Individuals who are deemed eligible based on responses to the stage 2 screening questions will proceed to screening stage 3 described below.
- 4.1.5.3 Screening Stage 3: Individuals will be contacted to schedule a date and time for the baseline interview. An RA will then conduct the baseline interview with the participant over the phone, where the MINI interview will be administered. All participants who complete the MINI interview will be compensated \$10 for completing the stage 2 screening questionnaires and an additional \$30 for completing the MINI interview. Payments may be made in either Amazon credits, by check or through Paypal depending on referral source, participant preference, NU payment policies, and payment availability at the time of study participation). Participants who are deemed ineligible after the MINI

- interview, will be thanked, sent a resource guide and compensated. If eligible following the MINI interview, participants will be randomized and enrolled in the study.
- **4.1.5.4** Study Enrollment: A research study assistant will work with participants to download the IntelliCare apps from the Google Play store, and if assigned to work with a coach, schedule the coach orientation call.
- **4.1.6** *Phase III Treatment Plan.* The IntelliCare intervention will be comprised of a combination of 3 components: (1) IntelliCare Treatment Apps, (2) IntelliCare Hub App, (3) and Coaching. A brief description of each component appears below.
  - 1. IntelliCare Treatment apps: There are 13 IntelliCare treatment apps. Each app instantiates a single behavioral strategy (e.g. scheduling positive behaviors, thought restructuring, goal setting, etc.), and takes only a few seconds to use. The apps address specific treatment goals, and may include didactic content as well as interactional components (e.g. activity scheduling/monitoring, thought records, etc.) that support behavior change. All participants will download the apps onto their own phones and use them daily during the 8 week intervention period.
  - 2. IntelliCare Hub app: The "Hub" app integrates the treatment apps and organizes the user's experience. We will be testing two different versions of the hub app; one with an intelligent recommender system (version A) and one without (version B). The recommender system in version A will use machine learning, which can learn from a patient's interactions with the intervention, to deliver and adapt treatment to the needs and preferences of the participant.
  - 3. Coaching: BA level coaches (supervised by a licensed psychologist), may support participants throughout the 8 week intervention period. We have developed a low-intensity coaching model that relies primarily on brief text messaging to promote engagement, along with one engagement orientation call at the beginning of treatment, and the option of a second call if needed.

While **all** participants will have access to the treatment apps during the 8-week intervention period, the version of the Hub app and the inclusion of coaching will vary for each participant according to random assignment to one of 4 groups:

```
Group 1 (n=75): Hub App Version A + Treatment Apps + Coaching
```

Group 2 (n=75): Hub App Version A + Treatment Apps + Independent Use (no coaching)

Group 3 (n=75): Hub App Version B + Treatment Apps + Coaching

Group 4 (n=75): Hub App Version B + Treatment Apps + Independent Use (no coaching)

At the end of the 8 week intervention, all participants will be informed that they may continue using the IntelliCare system on their phones but participants in groups 1 and 3 will no longer have access to their coach. For any participants who do continue app use after the study period has ended, the IntelliCare system will continue to collect app data as before.

4.1.6.1 Phase III Assessment, measures and compensation. RCT participants will receive trial assessments at baseline, week 4, and week 8 (post-treatment). Post-treatment follow-up evaluations will occur at 3 and 6 months to evaluate maintenance of gains. Assessments will consist of telephone based interviews and online self-report questionnaires. All assessments and evaluations will be conducted by an RA (i.e. coaches will not perform assessments on patients they coach). Depression will be measured at baseline by telephone interview using the MINI MDE module. Self-reported depression will be measured at baseline, wk4, wk8, 3 months post-treatment and 6 months post-treatment using the PHQ-9 administered online. Self-reported anxiety will be measured using the GAD-7 administered online at

baseline wk4, wk8, 3 months post-treatment and 6 months post-treatment. *Adherence* will be assessed through app use data from phone, including number of times the apps were accessed, number of times each app feature was accessed and percentage of messages viewed. Participants will be paid up to \$40 for the screening/baseline assessments, \$30 for the week 4 and 8 assessments, and \$30 for the 3 and 6 month assessments (total= up to \$160). Participants will not be compensated for using the apps or communicating with the study coach. Payments may be made in either Amazon credits or by check depending on participant preference, NU payment policies, and payment availability at the time of study participation. Individuals recruited through Focus Pointe Global will be paid through PayPal by Focus Pointe Global.

**4.1.7** *Phase II Study Retention.* Communication from the research study may occur across a participant's involvement in the trial to increase participant retention. Such contact could include sending greeting cards via mail or email (thank you, birthday, etc.) or sending small tokens of appreciation (keychains, pens, stress balls).

# 4.2 Confidentiality of Records- all phases

Study data will be kept in a locked, password protected databases stored on secure servers maintained by Northwestern University FSM IT. Participants' direct personal identifiers will not be released without prior consent except as specifically required by law. Efforts will be made to limit the use and disclosure of research study data to people who have a need to review this information. Study data may be shared for research purposes with collaborators outside of the research team at Northwestern University. Collaborators may include researchers at other institutions such as universities, foundations, research groups within companies, and/or government agencies for the purposes of improving the science by aggregating datasets across projects or accessing specialized expertise such as machine learning and data mining. A data use agreement will be established before study data is released to a researcher or organization that is not part of the study team. The data use agreement will specify what data will be transferred to another organization or research (see list of Data below). Some journals now require that data used in publications must be provided to the journal and may be made public. In those instances, we will provide a de-identified dataset to the journal. Study consent forms will explain the range of information that may be shared with collaborators.

#### 4.3 Data

- **4.3.1.1.1** *Adherence:* The primary adherence outcome will be length of time from initiating treatment to last use of treatment elements. We will also explore the motivational system by examining the number of motivational messages delivered, number viewed and the ratio of viewed/delivered by treatment arm. More specifically:
- **4.3.1.1.1.1** Messages include text and email messages between participants and study staff for the purposes of coaching and participant management.
- **4.3.1.1.2** App use includes the number, timing, and duration, application launches and launches of specific pages within the app.

- **4.3.1.1.2** *Depression:* Primary patient centered outcomes will use continuous measures of depression and anxiety.
- **4.3.1.1.2.1** *PHQ-9* will be used to evaluate self-reported depression. GAD-7 will be used to evaluate self-reported anxiety.
- **4.3.1.1.3** *Secondary Outcome Measures* will include the following (for a full list of self-report measures see Measures Appendix):
- **4.3.1.1.3.1** *Satisfaction*, measured using the USE questionnaire, which was designed to measure satisfaction, usefulness, ease of use, and ease of learning.

*Moderators and mediators* will include the measures provided prior to initiating treatment the Mini International Neuropsychiatric Interview, the SCT Motivation assessment, Behavioral Activation, wellbeing and quality of life, Coping, and

**4.3.1.1.3.2** Audiofiles include audio recordings of coaching and assessments. Audio files may be transcribed by one or more of the following NU transcription vendors:

GMR Transcription https://www.gmrtranscription.com/

Wordsworth https://wordsworthcoop.com

Files may be shared via secure access to FSM servers or through vendors' proprietary web-based applications for secure file management.

- **4.3.1.1.4** Coach generated notes on participant encounters.
- 4.4 Removal of Subjects from Study

Patients can be taken off the study treatment and/or study at any time at their own request, or they may be withdrawn at the discretion of the investigator for safety, behavioral or administrative reasons. The reason(s) for discontinuation will be documented and may include:

- 4.4.1 Patient voluntarily withdraws from treatment (follow-up permitted);
- 4.4.2 Patient withdraws consent (termination of treatment and follow-up);
- 4.4.3 Patient is unable to comply with protocol requirements; (termination of treatment and follow-up);
- 4.4.4 Patient demonstrates disease progression (termination of treatment and follow-up unless continued treatment with study intervention is deemed appropriate at the discretion of the investigator);
- 4.4.5 *Identification of Suicidality.* Suicidality will be monitored at all possible points of contact. It will be monitored by RAs at each assessment point (Field Trial: Baseline, Week 6, and Week 12. RCT: Baseline, Week 6, Week 12, Month 3, Month 6), using the QIDS-C and MINI module(s). Report of an elevated level of suicidal ideation (MINI Suicidality module score of 8 or greater or QIDS question 12 response of 12 score of 2 or greater at baseline; Positive response for MINI MDE section question A3.g or QIDS question 12 score of 2 or greater during later time points) will trigger administration of the CBITS Suicidality Protocol by the RA. Following a structured assessment of suicidal ideation by an RA, the information will be provided to a clinical monitor (Ph.D. level psychologist) who will review the information and take appropriate action (see below). One Ph.D. psychologist will be designated as

clinical monitor at all times. Suicidality will also be monitored in online self-report assessments. A score of 2 or greater on the PHQ-9 item 9 branches to the BDI-I item 9, which assesses for severity of suicidal ideation. Scores of 2 or greater on the BDI-I item 9 will trigger automatic and immediate notification to the RA who will attempt to contact the participant by phone, complete the CBITS Suicidality Protocol with direction and supervision by the Ph.D level clinical monitor as needed. Additionally, Coaches will be trained to identify potential suicidality in the coaching engagement telephone call or secure email communications, which will similarly result in administration of the CBITS Suicidality Protocol.. Information about suicidality will be discussed with the clinical monitor.

- Ensuring patient safety. Once the monitor (or any study clinician, who will serve as the monitor) is 4.4.6 notified of potential suicidality, the monitor will take all actions necessary to ensure patient safety. This includes: evaluation of all necessary data including study records, calling the patient for further evaluation, recommending hospitalization, calling emergency services in the participant's jurisdiction to perform a "health and safety" check, or any other actions deemed necessary to ensure the safety of the patient. The monitoring clinician also has the option of recommending that the patient be discontinued from the study and referred for more appropriate care. Because RAs are usually the main point of contact for patients, they will be given thorough training in the assessment of suicidality. While the clinical monitors will be responsible for the management of suicidal patients, it is possible that an emergent situation will arise that requires immediate attention. RAs (assessors and coaches) will be trained in the use of the CBITS Suicidality Protocol. This document includes a well-validated measure for assessing suicidal risk (Columbia Suicide Severity Rating Scale) and structured follow-up steps based on the participants' reported score. RA's will also standardly collect information regarding participants' current location when contacting the participant by phone in the case there is a need to contact emergency services. The PI will also be notified of all cases of suspected suicidality, will consult with the clinical monitor, and will be continuously updated. Any psychiatric problem rising to the level of an adverse event will be reported to the IRB and to the DSMB chair.
- 4.4.7 Patient Deterioration. Clinical deterioration as evidenced by an increase in the severity of depressive or psychiatric symptoms is the other potential risk. If the RA believes that a participant has deteriorated substantially either by showing a worsening in the presenting psychiatric symptoms or by the development of new psychiatric or treatment related symptoms, the clinical monitor will immediately be informed. The clinical monitor will evaluate the participant, notify the PI and DSMB, and make any necessary referrals for the care of the participant. If the PI, in consultation with the DSMB, determines it is in the participant's best interest to cease participation in the study, the patient will be terminated from the study, and referrals and assistance will be given in obtaining appropriate treatment. Reports will be filed with all necessary governing bodies, including the Northwestern University IRB and the DSMB.
- **4.4.8** Treating physician judges continuation on the study would not be in the patient's best interest;
- 4.4.9 Lost to follow-up. If a research subject cannot be located to document survival after a period of 2 years, the subject may be considered "lost to follow-up." All attempts to contact the subject during the two years must be documented and approved by the Data Monitoring Committee.
- 5 Adverse Event Monitoring
- 5.1.1 Adverse event data collection and reporting, which are required as part of every clinical trial, are done to ensure the safety of Subjects enrolled in the studies as well as those who will enroll in future studies using similar agents. Adverse events are reported in a routine manner at scheduled times during a trial. Additionally, certain adverse events must be reported in an expedited manner to allow for optimal

- monitoring of patient safety and care.
- 5.1.2 All patients experiencing an adverse event, regardless of its relationship to study drug/device, will be monitored until:
- 5.1.2.1 the adverse event resolves or the symptoms or signs that constitute the adverse event return to baseline;
- **5.1.2.2** any abnormal assessment ratings/observations have returned to baseline;
- 5.1.2.3 there is a satisfactory explanation other than the study intervention for the changes observed; or
- **5.1.2.4** death.

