- 6.9.2 Preliminary data indicates that approximately 50% of patients stop participating in BITs (which we define here as "drop out") by week 7 (see Sec. D.1.1). A sample size of 135/arm (total sample of 270) will provide 80% power to detect a difference in median drop out time from 7 to 10 weeks. We estimate from existing data (Sec D.1.1) that a 3 week increase would result in an 11% improvement in depression severity (ES=0.30). Additionally, this sample provides 80% power to detect an increase in continued participation from 50% to 61.6% at week 7. Both analyses are based on a log-rank test at a type 1 error rate of 5%, with accrual of 54 weeks and 12 weeks of intervention. Power for continuous patient

centered outcomes were based on independent t-tests, and would have 80% power to detect effect sizes of 0.34. Power calculations were performed using Pass 2008.(Hintze, 2008)

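### Sections 4.4.3 and 4.4.4 end follow-up as well as treatment for removal reasons that overlap with adherence and symptom severity, so PHQ-9/GAD-7 data may be lost for outcome-related reasons; the size is unknown.

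*Combined protocol and SAP*

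**What the plan says.** Section 4.4 lets participants leave at their own request, and adds that "they may be withdrawn at the discretion of the investigator for safety, behavioral or administrative reasons". The listed reasons carry different consequences for follow-up:

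- A voluntary stop of treatment (4.4.1) keeps the door open to measurement: "Patient voluntarily withdraws from treatment (follow-up permitted").
- Withdrawal of consent (4.4.2) ends both treatment and follow-up.
- Inability to comply (4.4.3) also ends both, with no exception. The entry reads "Patient is unable to comply with protocol requirements; (termination of treatment and follow-up").
- Worsening of the condition (4.4.4) ends both by default, and the one exception rests on the investigator's judgement. The wording here is "Patient demonstrates disease progression (termination of treatment and follow-up unless continued treatment with study intervention is deemed appropriate".
- Deterioration has a separate entry (4.4.7). The clinical monitor is informed first, and the PI then decides with DSMB input. The text for that decision is "determines it is in the participant's best interest to cease participation in the study, the patient will be terminated from the study".
- The treating physician's judgement (4.4.8) carries no stated follow-up consequence.

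On what is measured, section 4.1.6 expects that "All participants will download the apps onto their own phones and use them daily during the 8 week intervention period". The adherence outcome is time to last use (6.10.1). The patient-centered outcomes are continuous depression and anxiety scores, PHQ-9 and GAD-7 (4.3), collected online at baseline, weeks 4 and 8, and 3 and 6 months post-treatment (4.1.6.1). The only missing-data provision for the RCT is the remark in 6.11.1 that the mixed models can account for it.

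**The concern.** Stopping treatment and stopping measurement are separate decisions. Sections 4.4.3 and 4.4.4 join them for two groups whose outcomes are unlikely to be typical: participants who cannot comply, in a trial of adherence, and participants who get worse, in a trial of symptom severity. Whether a PHQ-9 or GAD-7 score exists at week 8 or later could then depend on what that score would have been.

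The loss need not be equal across arms. Objective 2.1.3 hypothesises that both factors improve adherence, so removals for non-compliance would be expected to differ. Only groups 1 and 3 have a coach, so non-compliance or worsening may also be noticed more often on one side of the coaching factor.

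A likelihood-based mixed model is valid when missingness depends only on recorded data, for example a high PHQ-9 already in the database. It is not protected when removal follows worsening between assessments, or staff judgement that leaves no trace in the modelled variables. The RCT sections state no missingness assumption, sensitivity analysis or as-randomised rule. At stake are bias in both factor comparisons and some power. Scores that are never collected cannot be recovered at analysis.

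**Working it through.** **1. The plan's own figure.** Section 6.9.2 gives 135 per arm and 80% power for a standardised difference of 0.34. A two-sided 5% two-sample t-test with 135 per arm has power 79.5% (normal approximation 79.8%), so the figure reproduces. With the 150 per factor level actually enrolled (300 in total, four groups of 75), power is 83.5%. That is the right no-loss reference below; the stated 80% belongs to 135.

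**2. Inputs for the illustration.**
- From 6.9.2: "approximately 50% of patients stop participating in BITs" by week 7, so retention p0 = 0.50, and p1 = 0.616 in the better arm.
- From 6.9.2: effect size 0.30, which the plan links to a three-week gain in participation, used here as the true total effect δ.
- Assumed, not in the documents: participants who keep using the apps do better by g = 0.5 to 1.0 SD, and a fraction f of stoppers lose follow-up, with f = 10%, 25%, 50% or 100%.

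**3. Shrinkage of a completer comparison.** The observed share in each arm is o = 1 − f(1 − p). The share of persisters among those observed is s = p / o. The observed difference falls short of δ by g × [(p1 − p0) − (s1 − s0)], where p1 − p0 = 0.116. Dividing by δ = 0.30:

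| f | s0 | s1 | s1 − s0 | Shrinkage, g = 0.5 | Shrinkage, g = 1.0 |
|---|---|---|---|---|---|
| 10% | 0.526 | 0.641 | 0.114 | 0.3% | 0.6% |
| 25% | 0.571 | 0.681 | 0.110 | 1% | 2% |
| 50% | 0.667 | 0.762 | 0.096 | 3% | 7% |
| 100% | 1 | 1 | 0 | 19% | 39% |

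Last row: 0.5 × 0.116 / 0.30 = 19%, and 1.0 × 0.116 / 0.30 = 39%.

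The planned mixed model recovers part of this. In a simulation with a week 4 to week 8 correlation of 0.6 and half of the effect present by week 4 (both assumed), shrinkage is about 2–4% at f = 50% and about 14–27% at f = 100%.

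**4. Power at 0.34.** The number observed per factor level is 150 × o:

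| f | Observed (lower vs higher retention) | Power |
|---|---|---|
| 0 | 150 vs 150 | 83.5% |
| 10% | 142.5 vs 144.2 | 82% |
| 25% | 131.3 vs 135.6 | 79% |
| 50% | 112.5 vs 121.2 | 73% |
| 100% | 75 vs 92.4 | 59% |

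**5. What the plan itself implies about loss.** 1 − 270/300 = 10%, although no RCT attrition rate is stated. If every stopper lost follow-up, about 50% and 38% of scores would be missing, which is far from 10%.

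This arithmetic addresses removal linked to stopping app use (4.4.3). It does not quantify removal for progression (4.4.4), for which the documents give no rate.

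**The case against.** The strongest reply is that 4.4 is a discretionary list, not an automatic rule. Participants may be withdrawn, inability to comply is not defined as low app use, and deterioration has its own route through the clinical monitor, the PI and the DSMB. The sample size leaves room for about 10% loss while expecting about half of participants to stop by week 7, so the authors evidently did not mean to end follow-up for every stopper. If removal follows a recorded score, the mixed model is adequate. All of this stands, and it limits the size. It does not alter the wording: once a participant is removed under 4.4.3, or under 4.4.4 without continued treatment, follow-up ends. Section 4.4.7 settles who decides, not whether questionnaires continue.

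Three stronger readings are tempting, and the documents do not support them.

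- **App-use outcomes also go missing.** Use is logged passively, 4.1.6 keeps collecting it from anyone who continues after the study period, and nothing stops logging at removal. Someone who has stopped has already had the event. What is absent is a rule on whether removal counts as an event or as censoring.
- **Follow-up survives only a voluntary stop.** Section 4.4.4 also keeps it where the investigator continues treatment, and 4.4.8 is silent.
- **Half of the scores will be lost.** That is the 100% row, an upper bound.

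**Conclusion.** The concern holds in a limited form. Two removal clauses end outcome collection, one outright and one by default, for reasons that overlap with adherence and symptom severity, and the plan says nothing that would protect the PHQ-9/GAD-7 comparison when removal rests on unrecorded worsening or staff judgement. Imbalance between arms is plausible from the plan's own hypotheses and from the coaching contrast, but it is not demonstrated.

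The size is unknown because no removal rate is given. If a quarter or fewer of stoppers lose follow-up, the illustration shows negligible shrinkage (2% or less) and power of 79–82%. The effect becomes material at half or more. These figures rest on the assumed persister advantage and on retention of 50% vs 61.6%. I also assume that the model in 6.11.1, which names PHQ-9, is meant for GAD-7 as well. Confidence in the textual point is good; confidence in any particular magnitude is low. The change is worth making because it is cheap and the lost data could not be recovered.

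**What to change.** Leave every treatment-stopping and safety decision as it is. Then:

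1. In 4.4.3 and 4.4.4, separate stopping treatment from stopping outcome collection. Scheduled online PHQ-9 and GAD-7 assessments (weeks 4 and 8, months 3 and 6) continue unless consent is withdrawn under 4.4.2. Section 4.4.1 already provides a model for the wording.
2. Reconcile 4.4.4 with 4.4.7, stating what happens to outcome collection for a participant whose participation is terminated because of deterioration.
3. State that all participants are analysed as randomised.
4. For time to last use, rely on the passive logs already collected and state whether removal is an event or a censoring.

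The cost is protocol wording, a few more online questionnaires and the associated payments. The existing PHQ-9 item 9 pathway in 4.4.5 would apply to these extra responses, so some research-assistant and clinical-monitor time should be allowed for.
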